4.2 SUBJECT POPULATION

Page 3 of 13

We will enroll 24 adult patients followed in the Kidney Clinic in AC-3 with chronic kidney disease. Evaluable subjects who withdraw from the study will be replaced to meet the enrollment goal. We will recruit patients of any gender, race, and socioeconomic status.

Vulnerable Subjects: We do not plan to include vulnerable subjects such as children, pregnant women, fetuses, or prisoners. Employees (physicians/fellows) will be assured that taking part in research is not a part of their duties, and refusing to participate in the study will not affect their job. To ensure their autonomy, the research coordinator (rather than the PI) will consent them.

5. INCLUSION AND EXCLUSION CRITERIA

Inclusion Criteria:

- Age \geq 18 years and \leq 80 years
- Estimated glomerular filtration rate (eGFR) \geq 25 and < 45 mL/min/1.73m²
- Able to provide consent
- Able to swallow Avmacol ES capsules

Exclusion Criteria:

- Significant co-morbid conditions with life expectancy of < 1 year
- Uncontrolled hypertension; an average recorded blood pressure ≥140/90 mmHg in the past 6 months
- Serum potassium of > 5.5 mEq/L at screening
- New York Heart Association Class 3 or 4 heart failure symptoms, known EF \leq 30% or hospital admission for heart failure within the past 3 months
- Factors judged to limit adherence to interventions based on appointment attendance and medication treatment compliance; PI will make this determination
- Current participation in another study
- Known to be pregnant or planning to become pregnant or currently breastfeeding; determined by self-report and medical record history. A urine pregnancy test will be completed for individuals of childbearing potential before administering the study drug.
- History of dementia documented in the medical record
- On anticoagulants or immunosuppression
- Under treatment for cancer

Non-English-speaking individuals will be not be included in Phase I of the study, but will be included in Phase II. If a patient cannot read, the consent form will be read to them by the research coordinator.

6. RECRUITMENT METHODS

Once eligible patients are identified, our research coordinator will reach out to each provider to ask them if we may speak with their patients for the study.

Phone/Video Call: The research coordinator will contact eligible patients by phone to introduce the study and gauge interest.

• If the patient is interested in participating, a follow-up phone or Zoom video call will be scheduled with the patient 7 to 10 days after the initial call and recruitment email is sent.

Page 4 of 13

Email: One recruitment email will be sent to eligible patients after the study is introduced by phone and the patient has verbally agreed to receive recruitment email communications. The study team member will obtain their permission to use email, per the following: "Because URMC can't control the security of email messages once we send them, we need your permission to email you. Do you want to receive the link to the consent via email?". Permission will be obtained before a PDF of the IRB approved consent form and study flyer is sent via email for their review.

The email will include a copy of the informed consent; a study flyer; an agreed time for a followup call, to occur either by phone or Zoom video, for the research coordinator to review the consent form and discuss the patient's participation further.

While the subject is on the phone, our research coordinator will provide the option of reviewing the consent form either by phone or via zoom. However, obtained/documented consent will occur in person as noted in Section 7.

Mail: Mailing the informed consent form with a cover letter that will instruct the potential subject not to sign/date the consent form as follow up phone or Zoom call will be made by the study coordinator to review with them. The consent will not be signed/returned via US postal; all consent will be obtained in person; refer to Section 7. Consent Process.

Flyer: Study flyers will be posted in Kidney Clinic in AC-3 and Highland Hospital clinic waiting area and restrooms. Subjects who contact the study team directly and leave voice mail will receive follow up phone call by the study coordinator, per the follow up recruitment phone script submitted for IRB review.

7. CONSENT PROCESS

- o Informed consent will be obtained by the research coordinator and documented via a signed consent form, and stored in a cabinet in a locked room.
- o The consent will be obtained in-person when the patient presents to the Kidney Clinic for their routine follow up.
- O To minimize coercion, the research coordinator, and not the patient's nephrologist, will explain to the patient the purpose of the study and go over the consent form, and give them the opportunity to ask questions. The patient will also be given the opportunity to take the consent form home with them and take as much time needed to look over the consent form.
- o If more time is requested by the patient, further follow-ups will occur over the phone to answer questions, concerns, and discuss participation.
- o The research coordinator will ask the patient to summarize the study to ensure their understanding.
- The Investigator or research coordinator will give a copy of the signed consent form to the subject and store the original appropriately in a cabinet in a locked room.
- A check-box for consent to contact subjects for future research will be an option with consent for this study.

Certificate of Confidentiality:

The study is funded by the National Institute of Health, and therefore the Certificate of Confidentiality (CoC) is automatically included as part of the notice of award. Language regarding the Certificate of Confidentiality will be included in the consent form.

8. STUDY PROCEDURES

Page 5 of 13

SCREENING PROCEDURES:

Avmacol ES has not been tested in patients with CKD. Since sulforaphane (SFN) and its metabolites are cleared by the kidney, to establish a safe dose for our study participants, for Phase I of the study, we will first perform PK analysis in CKD Stage 3B to 4 patients with eGFR between 25 - 45 mL/min/1.73m² who meet the inclusion criteria below. The eGFR result should be within a 2 week window at the time of screening. If eGFR testing was performed longer than 2 weeks, the research coordinator will reach out to the patient's provider to ask for repeat testing.

Our research coordinator will use eRecord EMR to screen patients for enrollment based on inclusion and exclusion criteria listed above in #5. Each week, the research coordinator (RC) will screen subjects scheduled to visit to the Kidney Clinic in the upcoming 1 to 2 weeks for enrollment. The RC will discuss with [name], who will make the final decision for inclusion and exclusion. If eligible and after subject consent is obtained:

A total of 2 in-person study visits will occur for the Phase I study. The first visit (AC3 or Highland Hospital) is expected to last for 1 hour. The second visit will only occur at the Clinical Research Center in Strong Memorial Hospital (SMH) and will take place on day 7 of taking the study drug and is expected to last up to 9-hours to allow biospecimen collections at 5 separate intervals.

RANDOMIZATION:

As noted in Section 4.1 Study Interventions, groups will be stratified by GSTM1 group, patients will be assigned randomly to 2 or 4 Avmacol Extra Strength tablets once a day, taken orally with food, as depicted in Table 1 (below). The groups are categorized into GSTM1 null (GSTM1 (0/0) or GSTM1 nonnull (GSTM1 (1/1) or (1/0)) genotype based on the dominant model we observed in AASK and ARIC cohorts. We do not anticipate difficulty obtaining the different genotype groups, as 75% of Caucasians are either GSTM1 (1/1) or (1/0), and 25 % are GSTM1 (0/0). Approximately 65% of patients in our Kidney Clinic are Caucasians. In African Americans/blacks, approximately 25% are GSTM1 (1/1), 50% are GSTM1 (1/0), and 25 % are GSTM1 (0/0). Approximately 30% of patients in our Kidney Clinic are African Americans. Randomization will be performed by the IDS who will be provided the patients' eGFR and GSTM1 genotypes. Since this is a PK study, the investigators will not be blinded to the randomization.

Visit 1 (1 hour) at AC3 or Highland Hospital Procedures:

Buccal Swab: A buccal (cheek) swab will be obtained from the subject to extract DNA for GSTM1 genotyping for assignment to groups as outlined in Table 1. (below). Genotyping will be performed as previously done ². The processing of DNA and genotyping will be completed within 5 business days.

Drug Dosing: In-person at the time of their study visit, patients in each dose group will be provided 2 or 4 tablets to be taken at home once a day with food for 7 days.

Table 1: Number of Avmacol Extra Strength Tablets Once a Day			
GSTM1 Genotype	2 Tablets	4 Tablets	
GSTM1 (1/1 or 1/0)	6	6	
GSTM1 (0/0)	6	6	

NIH

—— **Ouestionnaire:** For each subject, clinical status and symptoms will be monitored using this questionnaire for gastrointestinal symptoms. Paper copies of this survey will be administered to the subject at Visit 1 and each form is

Page 6 of 13

expected to take 20 minutes to complete. The questionnaire will be completed in-person as part of Visit 1, at home on Day 3, and returned with the next in-person visit on Day 7 (Visit 2).

Kansas City Cardiomyopathy Questionnaire (Modified): For each subject, clinical status and symptoms will be monitored using this questionnaire for heart failure symptoms. Paper copies of this survey will be provided to the subject at Visit 1 and are expected to take about 30 minutes each to complete. The questionnaire will be completed in-person as part of Visit 1, at home on Day 3, and returned with the next in-person visit on Day 7 (Visit 2).

General Questionnaire: Each patient will also complete a brief questionnaire of how they feel each day, including any new symptoms. Subjects are expected to complete the general questionnaire once each day throughout the 7-day period.

Subject Tracking Chart: For each subject, a chart will be provided to help track daily study drug intake and questionnaires. The form will also include the subject's study drug dosage and 7-day study timeline.

Visit 2/Day 7 Procedures (8-Hours) at Clinical Research Center in Strong Memorial Hospital:

On day 7, subjects will come to the Clinical Research Center at SMH, take their dose with food. This visit will last for about 8-hours in duration so samples of urine and blood samples can be obtained at scheduled time intervals. Food and drink will be provided for lunch during the 8-hour visit.

Subjects will be asked to return the drug package so the study team can account for the number of tablets taken during the 7-day period.

Blood Samples: Blood collection will involve one venipuncture 4 mL blood sample obtained at 0, 1 hour, 2, 4, and 8 hours. The samples may be obtained by a phlebotomist in the Clinical Research Center or Strong Memorial Hospital Outpatient Lab. An IV-line will be placed for the blood draws to minimize needle sticks. A total number of two collection attempts will be allowed for each time interval.

Urine Samples: Urine collection will involve one sample of a minimum of 1 mL of urine in a sterile cup obtained at 0, 1 hour, 2, 4, and 8 hours. Water will be provided between each sample collection.

Blood and urine will be obtained at 5 separate intervals listed above to determine SFN levels in plasma and urine, respectively. Whole blood, plasma, and urine at each time point will be obtained, frozen, and stored at -80°C for later processing and analysis. Levels of SFN and its active metabolites will be analyzed by our Mass Spectrometry Shared Resources Laboratory (MSRL) Core at the University of Rochester Medical Center.

Medical Record EMR: No research data (*GSTM1 genotype* or blood SFN level) will be included in the subject's medical record. Laboratory data that are part of the patients' clinical care will be conveyed to the patients as standard of care. For the study, we will collect demographic information, including age, sex, height, weight, race, past medical history – specifically history of hypertension, heart failure, and etiology of kidney disease, if any - and blood pressure data. Research data will not be conveyed to the patients. While not anticipated, incidental findings that might have health consequences for the individual subject will be addressed as clinically indicated.

As this is conducted under an IND, the samples will be stored for 2 years after marketing approval or for 5 years, whichever is later. Should additional tests be deemed informative or mechanistic to enhance Page 7 of 13

further understanding, we will contact the subjects while samples are still available.

Samples will be destroyed after 5 years.

Genetic Research Procedures: As mentioned above, the *GSTM1* null genotype is quite common in human populations, with 50% Caucasians and 27% African Americans being homozygous for the *GSTM1* (0/0) allele. Whole genomic sequencing will not occur. No genetic counseling will be provided to the subject. We will genotype *GSTM1* to assess whether it influences PK/drug metabolism of SFN from Avmacol.

Completion of the first phase: To ensure patient safety after they have completed or stopped the study drug, our research coordinator will call subjects after about 2 weeks to ask how they are feeling, and whether they have developed any new symptoms. If they have new symptoms, [name] will reach out to the patient to assess if further evaluation is warranted.

9. RISKS TO SUBJECTS

Sulforaphane/Avmacol ES (Study Drug)

There are some potential risks to participants since we are introducing a well-tolerated study drug in other clinical trials but has not been previously tested in CKD patients. We take careful precautions by first establishing an optimal dose of Avmacol ES in CKD patients using reported peak plasma concentrations in trials that were conducted in patients without kidney disease. Based on the multiple clinical trials that have been done with Avmacol or the actual sulforaphane compound in other diseases, we do not anticipate any serious risks. The most common side effects are gastrointestinal, including nausea and dyspepsia, which are ameliorated when taken with food.

Although not reported in any earlier trial, there is the possibility of an allergic reaction to the study drug. This reaction may be mild, such as a skin rash, or more severe symptoms like swelling of the throat, low blood pressure, and shortness of breath. In rare cases, a severe reaction could cause death.

Risks of Blood Draw

The most common risk is pain, bleeding, or bruising at the site of the blood draw. Other risks include redness, and swelling of the vein and infection, and a rare risk of fainting.

Risks of Buccal Swab

The risk is minimal. There is risk of not obtaining adequate sample for DNA extraction.

Risks of Urine Sample

The risk is minimal. There is risk of spilling urine onto clothes.

Risks of Pregnancy: The effect of sulforaphane on the fetus is not known. The patient will be advised to immediately stop taking the drug if pregnancy is suspected and notify the research team.

Risk of Disclosure of Privacy and Confidentiality

Other potential risks involve violations of confidentiality. Procedures for assuring confidentiality are discussed below.

Risks to Social/Emotional Well-Being

We do not anticipate any psychological, social or legal risks beyond those related to participation in a clinical study.

Page 8 of 13

Risks of Ouestionnaires

There are no anticipated risks for subjects to complete the requested questionnaires.

Patients will be informed that declining to participate in this study will not impact their care whatsoever.

10. POTENTIAL BENEFITS TO SUBJECTS

You might not benefit from being in this research study. Your participation will enable us to determine the best dose for the next study in patients with chronic kidney disease in which you would also be eligible to participate in.

11. COSTS FOR PARTICIPATION

There is no cost for participation of the study. Avmacol ES will be provided by Nutramax without cost to the patients.

12. PAYMENT FOR PARTICIPATION

Each of the study participants will receive \$100.00 in a prepaid Visa card, divided into two payments of \$50.00 at Visit 1 and Visit 2, as payment for their participation and completion of the study. Subjects who are withdrawn or voluntarily withdraw from the study due to side effects will also receive the full compensation of \$100.

13. SUBJECT WITHDRAWALS

- 1. Participants' decision to withdraw from the study for any reason
- 2. Development of side effects that are not resolved by dose reduction
- 3. Failure to adhere to the study protocol
- 4. Relocation resulting in inability to follow up per protocol
- 5. Become pregnant
- 6. New diagnosis of heart failure, cardiovascular event, life threatening infection, or cancer

In the event that a patient drops out the study due to reasons listed above, we will recruit an additional patient to replace.

Once treatment is stopped for any reason, patients will continue to be followed as part of standard of care for CKD. Long-term follow up data will continue to be collected, including their blood pressure, eGFR, and proteinuria.

RETURN OF RESULTS:

Once the study is completed, we will send subjects a summary of the results and what they mean. Subjects will not receive their own individual results.

14. PRIVACY AND CONFIDENTIALITY OF SUBJECTS AND RESEARCH DATA

The research team consists of URMC clinical providers (Nephrologists) and as such have access to all of the relevant clinic records. Study data will be collected and managed using REDCap electronic data capture tools hosted at URMC. Study data will be directly entered into REDCap which is a HIPAA

Page 9 of 13

compliant database. Only de-identified data will be analyzed, and de-identified data will be stored in a password protected database only available to the research team.

With regard to patient confidentiality, the risk of improper access, use, or disclosure of participant data is minimized through the following procedures:

- 1. All study personnel and researchers are required to sign a pledge of confidentiality, committing to safeguard the study data during its collection, analysis, and after the study is concluded.
- 2. Physical (paper) questionnaire forms and media containing the electronic data files will be kept in locked files with restricted access.
- 3. Data Key- Each subject will be assigned a study ID number which will be used to label their data/samples and linked to the subject on a separate key. Only [name] and the investigative team will have access to the data key and it will be stored separately from the dataset.
- 4. The data upon which statistical analysis will be conducted will contain participant numbers as unique identifiers in lieu of names, medical record number, or social security numbers. These data are considered identifiable, but not directly identifiable.

When data generated from this study is shared for analysis, only de-identified information will be exchanged. No protected health information will be shared with any collaborator nor used in any publications. Only aggregate results, not individual data, will be published in reports or manuscripts.

15. DATA / SAMPLE STORAGE FOR FUTURE USE

Samples will be collected, processed, and stored for future use in an approved -80°C freezer. To minimize costs, they will be run in batches based on the number of samples that can be loaded on commercially available kits. As this is conducted under an IND, the samples will be stored for 2 years after marketing approval or for 5 years, whichever is later. Only [name] and the investigative team will have access to the stored data and samples.

The investigative team may elect to share with other researchers and/or utilize subject data and biospecimens collected during this study for future research purposes. This includes subject samples, health information, and genotype GSTM1 data. Subjects will be provided the opportunity to opt-in or opt-out of permitting the study team to utilize their data and biospecimens during the ICF process. Should subjects agree to allow the study team to utilize data and biospecimens for future research, the data and biospecimens would be used to further understand kidney disease and other related topics.

The clinical data and associated biospecimens will be identified only by the Subject ID used in the current study. Computers housing the data are secured in locked rooms when not in use. All data files and derived analytic data files are encrypted for storage and transport. Study data will be kept on password protected computers at URMC, REDCap and UR Box program. Signed consent forms will be stored in a cabinet in a locked room.

- Harmonize the study data elements and variables from clinical and laboratory and biochemical data
- 5. Validate data quality and perform cleaning process.
- 6. Work closely with the PI and clinical investigators to determine appropriate statistical methods and machine learning algorithms for the clinical hypotheses. Cutting-edge statistical methods and innovative data science tools will be considered or adopted.
- 7. Prepare the analytical datasets and perform pre-stated statistical analyses.
- 8. Prepare the final results for manuscript writing and submission, conference presentations and publications.

The data for safety and feasibility assessment will be summarized descriptively with respect to adverse events and compliance with Avmacol ES intake. The group-specific data will be summarized and reported as mean \pm SD for continuous measures and as frequency and percentage for categorical measures and their differences will be compared using two-sample t-tests or Chi-square test.

18. PI oversight for multi-site research

The UR PI will be responsible for the following:

- A. Communication: The UR Pi will notify the Site PI of the RSRB site approval and provide site approval letter as well as copies of the most current version of the study materials via email. The UR PI is responsible throughout the course of the study to provide all modified documents and IRB approval letters to UVA site PI.
- B. Supervision of study activities at the site: The UR PI will conduct regular meetings with the site PI to review study activities. Meetings will occur every 3 months or sooner as soon as any issue arises by zoom. During the meeting, the UR PI will troubleshoot study-related issues, answer study-related questions, and provide verbal/written direction for all study activities. Meetings will be documented via meeting minutes in the regulatory binder.
- C. Training: The UR PI will ensure that all study personnel have completed required institution-specific and protocol-specific trainings and that these trainings are documented appropriately via CITI certification. When study personnel are added/removed, the UR PI will ensure UVA submits these changes to the local IRB for institutional review and approval. If applicable, these changes will be appropriately documented on the Delegation of Responsibilities Log.
- D. Reporting: The UR PI will submit required information for reporting, progress reports, reportable events, non-compliance, Data and Safety Monitoring reports and provide the site

Page 12 of 13

- with any RSRB determinations regarding the submitted reports.
- E. Site Files and Documentation: As per Policy 901 Investigator Responsibilities, all sites will maintain a regulatory file with current and accurate records of all study documentation as required by applicable regulatory requirements. These files are maintained electronically in secure BOX URMC servers and shared with study members only.

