4.1 STUDY INTERVENTIONS

STUDY DRUG: Avmacol Extra Strength capsules

IND # 158689

IND HOLDER: [name]

For Phase I, we will only use Avmacol ES, no placebo, to determine the PK of Avmacol ES in CKD to guide the dose used for Phase II.

Nutramax Laboratories, Consumar Care, Inc., will provide Avmacol ES capsules free of charge in bottles shipped directly to University of Rochester Medical Center (URMC) Clinical Research

Page 2 of 13

Pharmacy Investigational Drug Services (IDS). The IDS will store, monitor, and dispense the drug directly to subjects. Data from the study will be shared with Nutramax.

It should be noted that, compared to control, SFN at "low dose" or 0.5 μM concentration, ex vivo, is able to induce expression of the genes in human peripheral blood mononuclear cells (PBMCs) that encode the enzymes AKR1C1 and NQO1 that play a role in reducing radical species 5. Higher doses of 2 µM and 5 uM of SFN induce higher expression of AKR1C1 and NOO1, as well as HO-1. Other human trials with SFN have reported higher peak plasma concentrations of 1-2 µM ⁶.

GSTM1 genotype will first be determined for the PK analysis to assess whether the genotype influences

drug metabolism. Stratified by GSTM1 group, patients will be assigned randomly to 2 or 4 Avmacol Extra Strength tablets once a day, taken orally with food, as depicted in **Table 1**. The groups are categorized into *GSTM1* null (GSTM1 (0/0) or GSTM1 non-null (GSTM1 (1/1) or (1/0)) genotype based on the dominant model we observed in AASK and ARIC cohorts ^{2,3}.

Table 1: Number of Avmacol Extra Strength Tablets Once a Day				
GSTM1 Genotype	2 Tablets	4 Tablets		
GSTM1 (1/1 or 1/0)	6	6		
GSTM1 (0/0)	6	6		
0071117 (0/0)				

Between 800-900 patients are seen monthly in the URMC Kidney Clinic in AC-3 and Highland Hospital. Among these patients, ~ 60% have CKD Stage 3 or 4, and $\sim 40\%$ of the total patients are African American.

Table 2	Prevalence		
GSTM1 Genotype	Caucasians	African Americans	
GSTM1 (1/1 or 1/0)	50%	73%	
GSTM1 (0/0)	50%	27%	

The null genotype is quite common in human populations, with 50% Caucasians and 27% African Americans being homozygous for the GSTM1 (0/0) allele (see Table 2 for prevalence of GSTM1 genotypes) 7. We saw similar prevalence of genotypes in AASK and ARIC 2-4. Therefore, we do not anticipate difficulty identifying those with null versus non-null genotypes.

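### Section 17 gives the Visit 1 symptom scores no role; adjusting the 2 v 4 tablet comparison for them would gain precision at almost no cost (minor)

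*Combined protocol and SAP*

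**What the plan says.** **Design.** Section 4.1 states: "For Phase I, we will only use Avmacol ES, no placebo". Within GSTM1 strata, "patients will be assigned randomly to 2 or 4 Avmacol Extra Strength tablets once a day". Section 4.2 sets the size: "We will enroll 24 adult patients followed in the Kidney Clinic". Table 1 has four genotype-by-dose cells of 6. The dose is open: Section 8 says "the investigators will not be blinded to the randomization", and the patient's own tracking chart shows the dosage.

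**Symptom data.** Section 8 has the same schedule for the gastrointestinal questionnaire and the modified KCCQ: "The questionnaire will be completed in-person as part of Visit 1, at home on Day 3", with return at the Day 7 visit. It is not clear whether a further form is completed on Day 7 or only handed in. Patients also fill in a "brief questionnaire of how they feel each day, including any new symptoms" during the 7 days; no entry before treatment is mentioned.

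**Analysis.** Section 17 summarises safety and feasibility descriptively, by adverse events and compliance. It then gives means and SDs, or counts and percentages, by group, and "their differences will be compared using two-sample t-tests or Chi-square test". It names no questionnaire, time point, baseline, change score or covariate, and does not say whether a group is a dose or a genotype.

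**The concern.** Patients with an eGFR of 25 to 45 may have gastrointestinal complaints before the first tablet. Section 5 excludes the more severe forms of heart failure but not milder ones, so some patients may also score on the KCCQ at entry. The documents give no symptom frequencies, so this is a possibility and not a finding.

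Two questions depend on the Visit 1 score. The first is whether symptoms change on the drug at all. Without placebo, only the pre-treatment score speaks to that on these scales: if both doses caused the same nausea, the 2 v 4 comparison would show nothing. The second is whether 4 tablets are tolerated less well than 2. Randomisation makes that comparison fair, but in groups of 12 a t-test on the on-treatment score leaves explainable between-patient variation in the error term. One dose group may also, by luck, start with more symptoms.

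Because the dose is open and no questionnaire analysis is stated, the choice among on-treatment score, change and adjusted score could also be made after the data are seen.

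**Working it through.** **Inputs from the documents.** Table 1: 4 cells × 6 = 24, which agrees with Section 4.2 and gives 12 v 12 by dose. The plan states no alpha, power, SD or effect size for symptoms, so there is no power figure to reproduce.

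**Assumptions.** Two-sided alpha 0.05, 80% power, equal SDs, and a correlation r between Visit 1 and on-treatment scores of 0.3 to 0.8.

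**1. Chance imbalance at Visit 1.** SE of the difference in means = SD × √(2/12) = 0.41 SD.
- P(gap > 0.5 SD) = 2 × [1 − Φ(0.5/0.408)] = 22%.
- P(gap > 0.75 SD) = 2 × [1 − Φ(0.75/0.408)] = 6.6%.
- Average absolute gap = 0.80 × 0.41 = 0.33 SD.

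**2. Effect on an unadjusted on-treatment comparison.** A gap b shifts the expected difference by r × b. At r = 0.7:
- b = 0.5 SD shifts it by 0.35 SD; simulated type I error given that gap is 6%.
- b = 0.75 SD shifts it by 0.53 SD; simulated type I error given that gap is 16%.

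An opposite gap hides a true difference by the same amount. Over all randomisations, simulated type I error is 4.9% (r = 0.5) and 5.0% (r = 0.7). The test is therefore valid overall.

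**3. Gain from ANCOVA.** The residual SD is SD × √(1 − r²), so the SE falls by 1 − √(1 − r²). The detectable difference is (t₀.₉₇₅ + t₀.₈₀) × SE, which agrees with the noncentral t calculation:
- t-test, 22 df: (2.074 + 0.858) × 0.408 = 1.20 SD.
- ANCOVA, 21 df: (2.080 + 0.859) × 0.408 × √(1 − r²).

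| r | SE cut | ANCOVA detectable difference | Change-score detectable difference |
|---|---|---|---|
| 0.3 | 5% | 1.14 SD | 1.42 SD |
| 0.5 | 13% | 1.04 SD | 1.20 SD |
| 0.7 | 29% | 0.86 SD | 0.93 SD |
| 0.8 | 40% | 0.72 SD | 0.76 SD |

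The change-score column uses SD × √(2(1 − r)) with 22 df. A t-test on change is less precise than one on the on-treatment score when r is below 0.5, so ANCOVA is preferred between doses.

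**4. A small deduction.** Estimating the slope inflates the variance on average by about 1/(22 − 2) = 5%, or 2.5% on the SE. At r = 0.3 the net SE ratio is 0.954 × 1.025 = 0.98, a gain of about 2% rather than 5%. At r = 0.8 it is 0.60 × 1.025 = 0.615, so most of the gain remains. Adding the GSTM1 stratum leaves 20 df and barely moves the t quantiles.

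**The case against.** The strongest reply is that Section 17 is silent, not wrong. It does not say that raw on-treatment scores will be compared. A t-test on change from Visit 1 would fit its sentence, and the first task it lists is to develop the statistical analysis plan. That stands: the defect is an unstated analysis, and a reader who infers that the plan compares dose groups while ignoring baseline goes beyond the text.

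A reader might also infer that, with no placebo, Visit 1 is the only control for a dose effect, so that existing symptoms bias the 2 v 4 result. The documents do not support this. The doses are randomised and concurrent, and the overall error rate is nominal. The lack of placebo limits the drug versus no-drug question only. It would also be wrong to treat the shift at the edge of likely imbalance as typical. The 95% limit is 1.96 × 0.41 = 0.80 SD, which at r = 0.5 to 0.8 gives 0.40 to 0.64 SD. The average gap of 0.33 SD gives 0.16 to 0.26 SD, and the t-test's standard error already allows for such variation.

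Two further replies lower the weight of the point. Section 4.1 selects the Phase II dose on pharmacokinetic similarity, and no rule uses a questionnaire comparison. Sections 4.1 and 8 also ask patients about new symptoms, and Section 4.1 about worsening ones, which gives an informal baseline reference. Those reports do not adjust the questionnaire scores, however, so the gain from using Visit 1 remains.

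Finally, within-dose change in an open-label group cannot prove a drug effect, because expectation, time and regression to the mean remain. That is correct, and the report should say so.

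**Conclusion.** The point holds as a minor one. Section 17 gives no role to Visit 1 scores that Section 8 already collects, and names only two-sample tests for group differences. For drug versus no drug, Visit 1 is the only untreated reference on these two scales. For 2 v 4 tablets, what is lost is precision and protection against chance imbalance; there is no systematic bias.

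The size depends on a correlation that the documents do not give. Across 0.3 to 0.8 the SE falls by about 5% to 40% before the small slope-estimation cost, so the benefit is slight at the low end and substantial at the high end. The 0.41 SD and 22% follow from 12 v 12 and a normal approximation. That Visit 1 precedes dosing is a fair inference and is not stated outright: allocation needs a genotype from the Visit 1 swab, which takes up to 5 business days, yet Section 8 lists handing out tablets under Visit 1.

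**What to change.** In Section 17, for the gastrointestinal and modified KCCQ scores:

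- Define the comparison as 2 v 4 tablets and name the on-treatment time point, clarifying whether a form is completed on Day 7.
- Replace the two-sample t-test between doses with ANCOVA: on-treatment score on dose, with the Visit 1 score and GSTM1 stratum as covariates. Report the adjusted difference with a 95% confidence interval.
- Report mean change from Visit 1 within each dose group with a confidence interval, described as uncontrolled open-label change and not as proof of a drug effect.
- State that the Visit 1 forms are completed before the first tablet.

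The cost is wording, plus one degree of freedom for the Visit 1 score and one for the stratum (22 df becomes 20). No new data, visits or patients are needed.
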